### **Pilot study:**

It will conduct before data collection on 10% of patients to explore feasibility for future RCT, the efficiency, internal validity and fundamentally, the delivery of proposed trial and identify barriers and facilitators. **Mepilex Border Sacrum** dressings will be applied to 4 patients before the procedure and **Polyurethane foams (pink pad)** will be applied to 4 patients before the procedure. The data collection tool will be tested, and these patients will be excluded from the study, after completion the patient will have routine care for pressure ulcer treatment.

## **Effectiveness of polyurethane foam dressing compared with Mepilex dressing for pressure ulcer prevention in operating room: A randomized control clinical trial.**

### **Sample Size calculation:**

A Convenience sample of 80 cardiac surgery patients who are expected to have long procedures (more than 4 hours) will be included in this study. These patients will be divided randomly into two groups; the polyurethane foam (pink pad) group (40 patients), and Mepilex Border Sacrum dressings group (40 patients).

Ep-info program was used to find sample size using the following information:

Population size = 90 patients.

Expected frequency=50%.

Acceptable error=5%.

Confidence coefficient=99%.

Minimal sample size=79.

**Duration of the Study:** 6 months in total. The enrolment will be for 20 days. Follow up will be for maximum 7 days post operation for each subject. A period of 4 months will be for analysis and closing.

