## **Effectiveness of polyurethane foam dressing compared with Mepilex dressing for pressure ulcer prevention in operating room: A randomized control clinical trial.**

present study was designed to compare the effects of polyurethane foam (pink Pad) versus Mepilex dressing for prevention of pressure ulcer in operating room.

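### The sample-size calculation is a one-percentage survey formula; it gives no basis for the primary Pink Pad versus Mepilex comparison, whose precision is stated nowhere

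*Protocol*

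**What the plan says.** The Introduction closes with the aim: the "present study was designed to compare the effects of polyurethane foam (pink Pad) versus Mepilex dressing". The primary objective repeats this comparison. The only objective that concerns a single percentage is the secondary one, the incidence of postoperative pressure injury in the centre's cardiac surgery patients.

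The section on sample size first describes "A Convenience sample of 80 cardiac surgery patients", split into two randomised groups of 40. It then gives a calculation: "Ep-info program was used to find sample size using the following information". The inputs are "Population size = 90 patients", "Expected frequency=50" (per cent), "Acceptable error=5" (per cent) and "Confidence coefficient=99" (per cent), and the result is "Minimal sample size=79". The section gives no rate by arm, between-arm difference, margin, test level or power. No other section of the protocol does so either.

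**The concern.** The four inputs are those of a prevalence survey, whereas the trial's main question is a comparison of two arms. A reader looking for the trial's precision finds 5% at 99% confidence. That belongs to another question and looks far tighter than anything 40 versus 40 can deliver.

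The practical stake is how a result of no significant difference will be read. According to the Introduction, both products are already in use on these patients at the centre. Without a statement of what 40 per arm can distinguish, such a result could be taken to mean that either product will do.

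**Working it through.** **1. Reproducing the plan's figure.** Inputs from the sample-size section: N = 90, p = 0.5, d = 0.05, z = 2.5758 (99%, two-sided). One proportion with finite-population correction:

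n = N·p(1−p) / [(d/z)²(N−1) + p(1−p)] = 22.5 / (0.0335 + 0.25) = 79.36.

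This reproduces 79. At 95% confidence the same formula gives 73.1, so the stated 99% is what was used. No two-group quantity enters.

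**2. What the calculation does support.** For one pooled percentage with n = 80 and p = 0.5, at 99%:

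- Inference to the 90 patients only: 2.5758·√[(0.25/80)·(10/89)] = 4.8 points.
- Inference beyond them, without the correction: 2.5758·√(0.25/80) = 14.4 points.
- Sample size from the same inputs without the correction: 2.5758²·0.25/0.05² = 663.5, so 664.

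The 5-point precision therefore exists only because 80 of 90 people are nearly the whole group.

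**3. What 40 versus 40 gives for the comparison.** The protocol supplies no rates by arm, test or test level, so these are assumptions: 50% is its survey input, 29.5% is the upper literature figure in its Introduction, and 10% is a lower illustration. The level is two-sided 5%, and all 40 per arm are analysed. The 95% half-width of the risk difference at equal rates is 1.96·√[2p(1−p)/40]:

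| Rate in both arms | Normal approximation | Newcombe |
|---|---|---|
| 50% | ±21.9 | – |
| 29.5% | ±20.0 | – |
| 10% (4 events per arm) | ±13.1 | ±14.4 |

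With four events per arm the Newcombe figure is the safer one. The Wilson limits for 4/40 are 3.96% and 23.05%, and √(6.04² + 13.05²) = 14.4.

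**4. Power.** Full enumeration of two binomials (40, 40), two-sided 5%. The table gives the highest rate in the better arm that still reaches 80% power:

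| Rate in the other arm | Fisher | Uncorrected chi-square |
|---|---|---|
| 50% | 18.5% | about 21% |
| 29.5% | about 5% | about 7% |
| 10% | none (power 21% even at 0%) | none (power 58% even at 0%) |

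As an illustration, a halving from 29.5% to 14.75% has 27% power by Fisher and 36% by chi-square.

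**The case against.** **The number is openly a convenience sample.** True, and this explains where 80 comes from. But the same section then says that a program was used to find the size and gives a minimum. Neither statement says what 40 versus 40 can show.

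**The detail may sit in an analysis plan not seen here.** That would answer an omission. Here the protocol itself states a calculation, and it answers a different question from the primary one.

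**It is only a pilot.** The pilot is a separate 4 + 4 patients who are excluded from the study. The 80 are the main trial.

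**The protocol claims neither power nor equivalence, and a larger trial may not have been possible.** The first part stands. The harm depends on how a result is later read, and the protocol's own analysis section commits only to descriptive summaries. As to the second, the protocol does not define the population of 90. If it is the accessible group, a two-arm calculation could hardly have led to a larger trial. This is why the remedy is a corrected justification and not more patients.

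**Stronger readings that a reader might infer.** One is that 79 is a miscalculation; it is not. Another is that any non-significant result would leave 14 to 22 points open in both directions. That holds only if the observed rates are equal. With a non-zero observed difference the interval reaches further on one side and less on the other.

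**Conclusion.** The point holds as a wrong justification. The stated calculation is arithmetically correct for estimating one percentage among 90 patients, and it has no bearing on the primary comparison. It can be tied at most to the secondary incidence objective, and only for those 90.

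The size of the gap is the contrast between the 5 points at 99% that the section displays and the roughly 14 to 22 points at 95% that 40 versus 40 would leave for the risk difference at equal rates of 10% to 50%. These figures rest on assumed rates, level and tests. They are also a best case: several sections remove patients who die or change care setting, and the section on data management says that data after a death will not be used.

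The documents do not support the further conclusion that the trial fails a power target or must be enlarged. The protocol sets no target difference, so no single correct sample size follows from it.

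**What to change.** Keep 40 per arm and reword the sample-size section:

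1. Say that 80 is a convenience (feasibility) number.
2. Tie the survey figures at most to the secondary incidence objective, for the group of 90, and stop presenting them as the basis for the comparison.
3. State what 40 versus 40 gives, labelled as assumptions. Possible text: *If all 40 patients per arm are analysed, the 95% confidence interval half-width for the risk difference at equal rates is about ±14 points at 10% incidence (Newcombe), ±20 at 29.5% and ±22 at 50% (normal approximation). With a two-sided 5% test, 80% power needs the other arm at about 5% or lower (Fisher) or 7% or lower (uncorrected chi-square) when one arm is at 29.5%, and at about 18.5% or lower (Fisher) or 21% or lower (chi-square) when one arm is at 50%. Exclusions after randomisation make these figures worse.*
4. State that a non-significant result is not evidence that the two products are equivalent.

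If the sponsor has a target difference in mind, stating it with its power at 40 per arm would serve as well for item 3.

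The cost is the rewriting of one section, with no extra patients or procedures. The downside is that the stated precision becomes visibly less favourable.

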### **Setting:**

This study will be carried out at the operating room, cardiac surgery intensive care unit and cardiac surgery ward at King Abdullah Medical City, Holy Makkah.

### **Data Collection and Management:**

After the official approval from KAMC IRB and the local authority approval. All the research nurses had taken part in designing the protocol and had specific training in research methodology and prevention, treatment, and classification of PU. The principal investigator will convene a meeting with

## **Effectiveness of polyurethane foam dressing compared with Mepilex dressing for pressure ulcer prevention in operating room: A randomized control clinical trial.**

the study team to provide an overview of the study's implementation, with the aim of ensuring adherence to quality standards and regulatory requirements. Researchers will explain the study to the participants and take written consent if they want to participate. In cases where a patient is unconscious, written consent will be obtained from their Legally Acceptable Representative in accordance with legal protocols. Voluntary and anonymous participation will be ensured. In case of passing away the collected data will not be used, and safety reports will be submitted as per the local gaudiness. The data collection sheets will be securely stored in a locked file cabinet under the custody of the researchers.

### **Study outcome measurement:**

Data will be collected through one tool that will be collected by the assessor. It will include two sections as follows:

#### **Section I: Patients' demographic data**

This section was developed by the PI based on relevant literature. It will include demographic and medical history data will be collected from the patients' medical records without identifier such as age, sex, body mass index, history of smoking, diagnosis at the time of admission, and laboratory parameters including erythrocyte sedimentation rate (ESR) and C-reactive protein (CRP) will be recorded. Nutritional status of patients will be evaluated considering route of nutritional support (enteral or parenteral). Subject will be identified via serial codes.

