## **Effectiveness of polyurethane foam dressing compared with Mepilex dressing for pressure ulcer prevention in operating room: A randomized control clinical trial.**

DTPIs exhibit a discernible pattern of evolution. Initially, the affected area manifests abruptly as intact skin that exhibits discoloration, either in the form of purple or hyperpigmentation [2]. The lesions evolve into slender vesicles atop a dusky ulceration site, transforming into black eschar. Subsequently, the DTPI becomes unsealed, exposing a pressure injury that has penetrated through the entire thickness of the skin and underlying tissues, indicating a stage 3 or 4 injury [3,4]. According to a study conducted in 2013, it has been observed that wounds of this nature have the potential to heal without any loss of tissue. Nevertheless, it is imperative to provide sustained care and attention to prevent any deterioration [5].

Patients undergoing cardiac surgery are among those at the highest risk of developing PIs, with an incidence as high as 29.5% [6]. Among patients undergoing cardiac surgery, specific risk factors for PI include protracted exposure to pressure during lengthy surgical procedures, vascular disease, and/or postoperative vasopressor use [7]. The high incidence of PI among cardiac surgery patients suggests that conventional methods for preventing PI are inadequate for this population.

There are an increasing number of studies evaluating the efficacy of different dressings (typically multilayer foam dressings) in preventing pressure ulcers (PIs) of the sacrum, heel, and those related to medical devices in ICU and trauma patient populations [8,9]. Recent high-quality randomized controlled trials demonstrated that the use of specialty foam dressings over the sacrum can reduce the incidence of pressure ulcers in intensive care unit (ICU) patients and high-risk nursing home residents [10,11].

Although limited in design and/or sample size, additional research and quality improvement investigations support the efficacy of this intervention in preventing the formation of PIs [12]. The National Pressure Ulcer Advisory Panel, in collaboration with European and Pan-Pacific peer organizations, added a recommendation (with a "B" strength of evidence) to "consider applying a

[figure not shown]
- 2 -

Title: Effectiveness of polyurethane foam (pink pad) compared with Mepilex dressing for pressure ulcer prevention in operating room

Version: 2.0 (20-Jun-2023)

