### **Inclusion Criteria:**

- Subjects  $\geq 18$ .
- Willing to participate.
- Patients undergoing cardiac surgery.
- Patient who is at risk for PU development as measured with Braden scale.

- 4 -

Title: Effectiveness of polyurethane foam (pink pad) compared with Mepilex dressing for pressure ulcer prevention in operating room

Version: 2.0 (20-Jun-2023)

Effective date: 15-Aug-2023

Expiration date: 15-Aug-2024

اللجنة المحلية لأخلاقيات البحث  
Institutional Review Board

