## **Effectiveness of polyurethane foam dressing compared with Mepilex dressing for pressure ulcer prevention in operating room: A randomized control clinical trial.**

There are two types of intervention available in King Abdullah medical city for operating room pressure ulcer prevention. **Polyurethane foams** (Pink Pad) are a single use system for use in surgical procedures. The system consists of a proprietary formulation for the pink foam pad, non-woven lift sheet, body straps, head rests, and boot liners. It aids hospital facilities in providing a safe and effective method of management of the patient for pressure ulcers and non-movement for patients in the Trendelenburg position.

**Mepilex Border Sacrum** dressings are self-adherent, multilayer foam dressings designed for use on sacrum aiming to prevent pressure ulcers. The dressings are used in addition to standard care protocols for pressure ulcer prevention.

After getting official permission from KAMC IRB, the subject will be randomized using electronic randomization 1:1 ratio. The randomization list was generated electronically through R using the Random Allocation Rule. Patients will equally be allocated into 2 groups randomly. The polyurethane foam group and Mepilex Border Sacrum dressings group.

**Standard PUs preventive care** - All included patients received standard PU prevention according to hospital protocols, based on contextualization and adaptation of International guidelines ( European Pressure Ulcer Advisory Panel, 2021 ), which involved: assessment of PU risk through the Braden Scale at hospital admission, every seven days and when clinically indicated (for example after surgery); full skin assessment during every shift, three times per day combined with routine positioning every 2 h or when required; use of active support surfaces (higher- specification foam mattress or dynamic anti-decubitus mattress) in case of Braden < 16, aiming at preventing damaging tissue deformation and providing an environment that enhances perfusion of at risk tissues; incontinence skin care.

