### **Statistical Analysis Plan**

Data obtained from the study will be coded and transformed into coding sheets. The results will be checked. Then, the data will be entered into SPSS system files (SPSS package version 22). Following data entry, checking and verification will be done to avoid errors during data entry. Finally, analysis and interpretation of data will be conducted. Categorical variables will be expressed as number and percentage while continuous variables will be expressed as mean and standard deviation.

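### The pre-operative Braden score, used for entry and taken in every patient, is not named on the data sheet and has no role in the stated analysis, so precision and a check on baseline risk are given up

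*Protocol*

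**What the plan says.** The Braden score is the protocol's own measure of ulcer risk and appears in two places. Inclusion Criteria require a "Patient who is at risk for PU development as measured with Braden scale", with no cut-off given. Under Study Procedure, standard preventive care includes "assessment of PU risk through the Braden Scale at hospital admission, every seven days and when clinically indicated", and active support surfaces are used "in case of Braden < 16".

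The trial's data come through one tool with two sections. Section I takes demographic and medical-history data from the records, given as examples: "age, sex, body mass index, history of smoking, diagnosis at the time of admission, and laboratory parameters including erythrocyte sedimentation rate", followed by CRP and route of nutrition. Braden is not named. Section II is the BWAT wound form, completed only if an ulcer occurs.

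Randomization describes a simple electronic list made by the Random Allocation Rule, 1:1, with no stratification factor. Sample Size calculation sets 40 patients per arm. The protocol's section headed Statistical Analysis Plan is descriptive: "Categorical variables will be expressed as number and percentage", with means and standard deviations for continuous variables. It names no covariate and no between-arm comparison.

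**The concern.** The protocol names ESR, CRP and smoking as baseline data but not the one scale by which it defines risk. What goes on the data sheet is a protocol matter. A later analysis plan can tabulate or adjust for a score only if the trial has captured it.

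Two things are at stake. The first is interpretation: with 80 patients and no stratification, a reader will want to know whether the arms began at similar ulcer risk, and the named fields do not show this on the protocol's own measure. Because the entry threshold is unstated, the recorded score is also the only way to see who counted as at risk. The second is precision: if the score predicts ulcers in this sample, adjusting for it would sharpen the comparison without adding patients.

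**Working it through.** **The plan's own figure.** Inputs from Sample Size calculation: population 90, expected frequency 50%, error 5%, confidence 99%.

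- n0 = z²p(1−p)/d² = 2.576² × 0.25 / 0.0025 = 663.5
- With finite-population correction: 663.5 / (1 + 662.5/90) = 79.36, the stated 79.

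The figure reproduces. It is a precision calculation for a single proportion and says nothing about balance or power between arms.

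**Chance of imbalance.** Put 40 of the 80 patients in a higher-risk Braden half (assumed). Under a 40/40 allocation rule, the number X of these in one arm is hypergeometric(80, 40, 40).

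- 23/17 or worse, a gap of at least 6/40 = 15 points: P = 0.263
- 24/16 or worse, a gap of at least 8/40 = 20 points: P = 0.117
- 22/18 or closer: P = 1 − 0.263 = 0.737

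If the higher-risk group is 30% to 50% of patients, the first two probabilities run from 0.22 to 0.26 and from 0.09 to 0.12. For a continuous score, the standardised difference has SD √(2/40) = 0.224, so P(|difference| > 0.25) = 0.26 and P(> 0.5) = 0.025.

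**Effect of a 24/16 split on the result.** The shift with no product effect is (8/40) × (risk in worse half − risk in better half). Overall risk is set at 29.5%, the upper incidence in the Introduction, which is not a design input. The gaps are assumptions. R² = (gap/2)² / (0.295 × 0.705), and the equivalent sample size is 80/(1 − R²). The mean absolute gap between arms over all allocations is 8.84 points, so the mean shift is 0.0884 × gap.

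| Assumed risk gap | Shift at 24/16 | Mean shift | R² | Equivalent N |
|---|---|---|---|---|
| 10 points | 2.0 | 0.9 | 0.012 | 81 |
| 21 points (40% v 19%) | 4.2 | 1.9 | 0.053 | 84 |
| 31 points (45% v 14%) | 6.2 | 2.7 | 0.116 | 90 |
| 41 points (50% v 9%) | 8.2 | 3.6 | 0.202 | 100 |

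For scale, the standard error of the unadjusted difference is √(2 × 0.295 × 0.705 / 40) = 10.2 points.

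**Power with and without adjustment.** This was simulated with 4,000 runs per row, 40 per arm, logistic likelihood-ratio tests and two-sided 5% level. The protocol gives no effect size, alpha or Braden association, so all of these are assumptions. Each cell shows unadjusted, then adjusted.

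| OR per SD of Braden | 29.5% v 10% | 29.5% v 15% | No effect |
|---|---|---|---|
| 1.0 | 63.2, 63.4 | 35.7, 36.2 | 5.3, 5.5 |
| 1.5 | 60.7, 62.9 | 35.8, 37.3 | 5.7, 5.7 |
| 2.0 | 62.4, 66.2 | 35.2, 38.5 | 5.2, 5.3 |
| 3.0 | 60.6, 68.9 | 35.4, 40.8 | 5.8, 5.6 |

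The gain runs from 0.2 to 8.3 points. Type I error is 5% to 6% either way.

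**Events available.** With 29.5% in both arms, 80 × 0.295 = 23.6 events. With 29.5% v 10%, 11.8 + 4 = 15.8 events. That supports one covariate, not several.

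**The case against.** **The list is illustrative.** Section I introduces its fields as examples, so the claim that Braden is absent from the data sheet goes too far; it is only not named. The score also stays in the hospital record and could be retrieved. Both points stand. They weaken the charge of lost data but do not remove the case for naming the field, since less central items are named.

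**Covariate models belong to an analysis plan.** A separate plan may exist, and the absence of an adjusted model would alone be a weak finding. This is accepted; the weight rests on recording the score.

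**Chance imbalance is not bias.** A reader might infer that an unstratified, unadjusted comparison is invalid. It is not: its type I error holds, and its standard error already allows for such imbalance. Even the largest shift in the table, 8.2 points, is below one standard error of 10.2.

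**The larger shifts are not the typical ones.** They use a split that, at that size or worse, occurs in 12% of allocations, with a strong assumed association. Entry restricted to at-risk patients, and support surfaces triggered by low scores, could both weaken the association here. This stands, which is why the 10-point row and the odds ratio of 1.0 are shown.

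**Other risk factors.** The Introduction says that "specific risk factors for PI include protracted exposure to pressure during lengthy surgical procedures, vascular disease, and/or postoperative vasopressor use". A reader might count all three as omitted baseline fields. The documents do not support that. Operation length and vasopressor use arise after randomisation, and the sample is already limited to operations expected to exceed 4 hours. Vascular disease may fall under the medical history or admission diagnosis that Section I collects.

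**Conclusion.** The point holds as one about recording and precision. The protocol relies on the Braden score for entry and has it for every patient, but does not name it as trial data, stratify on it or give it a role in the stated analysis. The primary comparison remains valid. What is missing is a view of baseline balance on the protocol's own risk measure, and some precision.

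A 23/17 or worse split of the higher-risk half has probability 26%, and 24/16 or worse 12%; these follow from the 40/40 design and an assumed median split. The gain from adjustment is less certain, from almost nothing to about 8 points of power, and depends wholly on the assumed odds ratio per SD of 1.0 to 3.0, event rates and 5% level.

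A reader might also infer that adjustment would remove the imbalance at no cost. It would not: it addresses only the measured factor, gains little if the score is weakly prognostic, and is strained when events are few.

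**What to change.** 1. Name the last pre-operative Braden total score as a field in Section I, and tabulate it by arm.
2. Prespecify it as the single covariate in the primary between-arm comparison of any new ulcer by day 7. Report a standardised risk difference with 95% CI, with the unadjusted difference beside it.
3. Fix one estimation method in advance that tolerates few events, for example penalised logistic regression. Do not switch the primary estimator on the observed event count, because that makes the analysis depend on the outcome data. At 10% incidence there would be only about 8 events (80 × 0.10), so the chosen method must cope with that.

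The cost is one value copied from the chart per patient and a sentence or two of analysis text. The randomisation list need not change, and no clinical care is altered. The downside is small: with few events the adjustment may gain little.
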